17.7.2.7.5 Investigational medicinal product packaging and labeling

See [Section 8.5](#).

17.7.2.7.6 Storage conditions and shelf life

See [Section 8.6](#).

17.7.2.7.7 Responsibilities

See [Section 8.7](#).

17.7.2.7.8 Concomitant medication

See [Section 8.8](#).

17.7.2.7.8.1 Prohibited concomitant medication

The following concomitant treatments are not permitted during the Screening Period or during the Treatment Period:

- SCS for treatment other than severe exacerbation of asthma and/or high-potency topical steroids within 30 days before the screening visit (Visit 0), during the screening period, and/or during the treatment phase of this study. Intra-articular steroids are not allowed to be used in the above mentioned period.
- IgE therapy (eg, omalizumab) within 130 days or interleukin-5 antagonist (e.g. mepolizumab) within 110 days prior to screening visit (Visit 0), or any other biologic therapy/immunosuppressant to treat inflammatory disease or autoimmune disease within 2 months prior to screening visit (Visit 0).
- Allergen immunotherapy (except if initiated more than 3 months prior to Visit 0 and dose stable 1 month prior to Visit 0).
- IVIG therapy.
- Live Attenuated Vaccines: refer to [Appendix B](#). Live (attenuated) vaccines are allowed in the screening period, if taken at least 4 weeks prior to the administration of the first dose of investigational medicinal product (ie, at least 4 weeks prior to visit 1).

- Asthma relievers other than salbutamol/albuterol: their use is not recommended unless in exceptional circumstances during the study period (eg, prescribed by a physician not participating in the study).
- Exposure to another antibody within a time period prior to Visit 0 that is less than 5 half lives of the antibody. In case the half-life is not known, then the minimum interval since exposure to the prior investigative antibody is 6 months. The minimum interval since exposure to any other (non-antibody) investigative study medication is 30 days prior to Visit 0.
- Any investigational treatment and procedure.

17.7.2.7.9 Cautioned concomitant medication (Cytochrome P450 enzyme substrates)

See [Section 8.8.2](#).

17.7.2.8 Assessment of investigational medicinal product

17.7.2.8.1 Primary endpoint

The primary endpoint in the Japan substudy is change from baseline in % predicted FEV1 at Week 12.

17.7.2.8.2 Secondary endpoints

The secondary efficacy endpoints of this study are:

- Annualized rate of severe asthma exacerbation events, during the treatment period.
- Change from baseline in pre-bronchodilator % predicted FEV1 at Weeks 2, 4, 8, 24, 52, and 64.
- Change from baseline in other lung function measurements (absolute FEV1, FVC, FEF 25-75%) at Weeks 2, 4, 8, 12, 24, 52, and 64.
- Change from baseline at Week 2, 4, 8, 12, 24, 36, 52, and 64 in ACQ-IA.

See [Section 9.2.1.1](#) on assessment of severe asthma exacerbation.

17.7.2.8.2.1 Assessment of lung function by spirometry

Lung function parameters will be assessed by centralized spirometry at screening visit (Visit 0), Visit 1 (Week 0), Visit 2 (Week 2), Visit 3 (Week 4), Visit 4 (Week 8), Visit 5 (Week 12), Visit 8 (Week 24), EOT (Week 52), and EOS visits (Week 64).

A spirometer that meets the 2005 American Thoracic Society (ATS)/European Respiratory Society (ERS) recommendations will be used. Spirometry should be performed in accordance with the ATS/ERS guidelines ([8](#)). For prebronchodilator measured parameters, including FEV1, peak expiratory flow (PEF), FVC, and FEF 25% to 75%, spirometry will be performed after a wash out period of bronchodilators according to their action duration, for example withholding the

last dose of salbutamol/albuterol for at least 6 hours, withholding the last dose of LABA for at least 12 hours (ultra-LABA like vilanterol should be withheld for at least 24 hours), and withholding the last dose of LAMA for at least 24 hours.

At all related visits, spirometry will be performed either in the AM or PM, but preferably in the AM, and at approximately the same time at each visit throughout the study. The same spirometer and standard spirometric techniques, including calibration, will be used to perform spirometry at all visits and whenever possible, the same person should perform the measurements.

Pulmonary function tests will be measured in the sitting position; however, if necessary to undertake the testing with the patient standing or in another position, this should be noted on the spirometry report. For any patient, the position should be consistent throughout the study.

Three measurements fulfilling the ATS acceptability and repeatability criteria should be obtained at every visit, if possible. The acceptability criteria must be applied before the repeatability criteria. Unacceptable maneuvers must be discarded before applying the repeatability criteria. If a patient fails to provide repeatable and/or acceptable maneuvers, an explanation should be recorded.

The largest FEV1 and largest FVC should be recorded after the data are examined from all of the acceptable curves, even if they do not come from the same curve. The FEF 25% to 75% should be obtained from the single curve that meets the acceptability criteria and gives the largest sum of FVC plus FEV1 (best test).

Automated best efforts, which combine FEV1 and FVC are not acceptable.

The spirometer must be calibrated following the principles of the ATS/ERS guidelines every day that a study patient is seen and spirometry is carried out. The calibration records should be kept in a reviewable log. It is preferred that the calibration equipment (that is 3-liter syringe) that is used to calibrate the spirometer be subjected to a validated calibration according to the manufacturer's specifications.

Further details on spirometry will be available in a separate operational manual provided to the sites.

17.7.2.8.2.2 Asthma Control Questionnaire–Interviewer Administered

The ACQ-IA was designed to measure both the adequacy of asthma control and change in asthma control, which occurs either spontaneously or as a result of treatment, and will be used for children 6 years to <12 years old at screening.

ACQ-7-IA (Asthma Control Questionnaire–Interviewer Administered, 7-question version)

The Asthma Control Questionnaire–Interviewer Administered, 7-question version (ACQ-7-IA) has 7 questions, with the first 5 items of ACQ-7 (ACQ-5-IA score) addressing the most common asthma symptoms: 1) frequency in past week awoken by asthma during the night, 2) severity of asthma symptoms in the morning, 3) limitation of daily activities due to asthma, 4) shortness of breath due to asthma and 5) wheeze. And with 2 questions on overall reliever medication use

6) short-acting bronchodilator use, and – after spirometry assessment – current asthma status;
7) predicted bronchodilator use of FEV1 (pre-bronchodilator use, % and % predicted use).

Patients and/or parent(s)/caregiver(s)/legal guardian(s) are asked to recall how their asthma and/or their child's asthma, respectively, has been during the previous week and to respond to the symptom and bronchodilator use questions on a 7-point scale (0 = no impairment, 6 = maximum impairment). Clinic staff scores the % predicted FEV1 on a 7-point scale based on the pre-central reading spirometry result displayed immediately after the spirometry testing. Then, the questions are equally weighted and the global ACQ-7 score is the mean of the 7 questions and therefore between 0 (totally controlled) and 6 (severely uncontrolled) (see [Section 17.7.2.15](#)).

Higher score indicates lower asthma control. Patients with a score below 1.0 reflect adequately controlled asthma and patients with scores above 1.0 reflect inadequately controlled asthma. On the 7-point scale of the ACQ-7, a change or difference in score of 0.5 is the smallest change that can be considered clinically important, corresponding to the MCID defined by the developer.

For statistical analysis, ACQ-7 global score is calculated by the sponsor using the BMS post central reading value of the %predicted FEV1 for the question 7 of the questionnaire.

Measurement properties such as reliability and ability to detect change have been documented in the literature ([10](#)).

ACQ-5-IA (Asthma Control Questionnaire–Interviewer Administered, 5-question version)

The ACQ-5-IA will be deduced from the responses to the first 5 questions of ACQ-7-IA and will be used for children ≥ 6 years to <12 years old at screening and baseline for eligibility evaluation.

Higher score indicates lower asthma control. Patients with a score below 1.0 reflect adequately controlled asthma and patients with scores above 1.0 reflect inadequately controlled asthma. On the 7-point scale of the ACQ-5, a change or difference in score of 0.5 is the smallest change that can be considered clinically important, corresponding to the MCID defined by the developer.

Measurement properties such as reliability and ability to detect change have been documented in the literature.

17.7.2.8.3 Other secondary endpoints

17.7.2.8.3.1 Long-term safety and tolerability

Long-term safety and tolerability for this study is the number (n) and percentage (%) of patients experiencing any TEAE during total study periods (definition see [Section 10.4.1.1](#)).

Additional analyses will describe the number (n) and percentage (%) of patients experiencing any:

- Serious adverse events (SAE definition refers to [Section 10.4.1.2](#)).
- Adverse events of special interest (AESI definition refers to [Section 10.4.1.3](#)).
- Adverse events related to IMP.

- Adverse events leading to permanent IMP discontinuation.
- Adverse events other than ISR.

Adverse events, including SAEs and AESI, will be collected at any time during study starting from signed consent form. The Investigator will ask the patient and parents how he/she has felt since the last study visit.

The Investigator should take all appropriate measures to ensure the safety of the patients. Notably, he/she should follow up the outcome of SAEs/AESI until clinical recovery is complete and laboratory results have returned to normal or until progression has been stabilized or death. In all cases, this may imply that observations will continue beyond the last planned visit per protocol, and that additional investigations may be requested by the Sponsor.

When treatment is prematurely discontinued, the patient's observations will continue until the end of the study as defined by the protocol for that patient.

In case of any SAE/AESI with immediate notification brought to the attention of the Investigator at any time after the end of the study for the patient and considered by him/her to be caused by the investigational product with a reasonable possibility, this should be reported to the Sponsor.

Adverse events for each patient will be monitored and documented from the time the patient gives informed consent/assent at Visit 0 until the EOS visit, except for:

- Serious adverse events.
- Adverse events that are ongoing at database lock.

Adverse events, AESIs, SAEs, AEs leading to IMP discontinuation and deaths will be reported as described in [Section 10.4.1](#) and analyzed as in [Section 17.7.2.10.4.3](#).

Laboratory tests, vital signs, physical examination, or electrocardiogram (ECG) abnormalities are to be recorded as AEs only if they meet the criteria defined in [Section 10.4.3](#), and are assessed as described in [Section 17.7.2.8.3.5](#), [Section 17.7.2.8.3.2](#), [Section 9.1.2](#) and [Section 17.7.2.8.3.4](#). In addition to assessment of primary endpoint, below parameters are used on an ongoing basis during the study to monitor safety of participants and will be presented in a descriptive manner.

17.7.2.8.3.2 Vital signs

Vital signs including blood pressure (mmHg), heart rate (beats per minute), respiratory rate (breaths per minute), and body temperature (degrees Celsius) will be measured at each onsite visit except for IMP administration only visits.

Vital signs will include height (cm) and body weight (kg). Height will be measured at each onsite visit except for the IMP administration only visit and Visit 9 (Week 36). Weight will be measured at each onsite visit except for the IMP administration only visit.

17.7.2.8.3.3 Physical examinations

See [Section 9.1.2](#).

17.7.2.8.3.4 Electrocardiograms

Electrocardiogram (ECG) variables will be recorded by a standard 12-lead ECG. ECGs will be performed at screening, EOT, and EOS (see [Section 17.7.2.2.2](#)).

17.7.2.8.3.5 Clinical laboratory values

Abnormal laboratory values that are considered to be clinically significant by the Investigator should be repeated as soon as possible after receiving the laboratory report to rule out laboratory error. Persistent abnormal laboratory values should be repeated until they return to normal or until an etiology of the persistent abnormality is determined.

Globally, guidelines for blood collection volume limits for pediatric studies range between 1% and 5% of total blood volume (TBV) for a single draw (or during a 24-hour period) and up to 10% of TBV over 8 weeks [\(9\)](#). Scheduled collections in the current protocol, for the smallest possible patient (15 kg), remain within this limit for every 3 months. For all scheduled blood collection visits, the total volume does not exceed 1.5 mL/kg for the smallest possible patient.

Refer to [Section 17.7.2.2.2](#) for the description of the clinical laboratory evaluations and the schedule of laboratory evaluations performed throughout this study. The clinical laboratory parameters that will be measured in safety are:

Hematology:

To include blood count (erythrocytes, hemoglobin, hematocrit, leukocytes), differential blood count (neutrophils, lymphocytes, monocytes, eosinophils, basophils), and platelets.

Serum chemistry:

To include creatinine, blood urea nitrogen, glucose, total cholesterol, total protein, albumin, total bilirubin (in case of values above the normal range, differentiation in conjugated and nonconjugated bilirubin), ALT, AST, ALP, electrolytes (sodium, potassium, chloride), bicarbonate, and CPK. Patients' fasting or nonfasting status at blood sample collection will be recorded on the Central Laboratory Requisition Form. Fasting is considered as no intake of food or any drink except for water for at least 8 hours.

Urinalysis:

Urinalysis will be conducted by dipstick during onsite visit. The parameters include pH, glucose, ketones, blood, protein, nitrate, leukocyte esterase, urobilinogen, and bilirubin (by dipstick). If any parameter on the dipstick is abnormal, further urine test is under Investigator's judgement.

Refer to [Section 17.7.2.2.2](#) (Study Flow Chart) for the schedule of urinalysis performed throughout this study.

Pregnancy test

A urine pregnancy test must be negative at Visit 0 and Visit 1 for enrolling girls who have commenced menstruating, and a urine dipstick pregnancy test will be performed at subsequent onsite visits prior to administration of IMP. In case of a positive urine test, a serum pregnancy test should be performed to confirm. Patients found to have a positive urine pregnancy test, confirmed by a positive serum pregnancy test will be excluded from the study. Patients with a false positive urine pregnancy test manifested as a positive urine pregnancy test but a negative serum pregnancy test will be allowed to be enrolled. Refer to [Section 17.7.2.2.2](#) (Study Flow Chart) for the schedule of pregnancy tests performed throughout this study. Those female patients who commence initial menstruation during the study will be similarly monitored with urine dipstick pregnancy tests and contraception consulting for the duration of the study.

Clinical laboratory testing at screening visit (Visit 0) will include HBs-Ag, hepatitis B surface antibody (HBs-Ab), HBc-Ab, HCV-Ab, HIV screen (Anti-HIV-1 and HIV-2 antibodies) and anti-nuclear antibody (ANA). For eligibility interpretation for hepatitis serology, refer to [Table 6](#).

Table 6 - Eligibility interpretation for hepatitis serology

Hepatitis Serology Result	Protocol Action
HBs Ag positive or indeterminate	Excluded
HBs Ab positive, HBs Ag negative, HBc Ab negative	Eligible
IgM HBc Ab positive	Excluded
Total-HBc Ab positive (with or without HBs Ab positive)	Test for HBV DNA 
• If HBV DNA positive: excluded• If HBV DNA negative/not detected^a: eligible
HCV antibody positive	Test for HCV RNA 
• If HCV RNA positive: excluded• If HCV RNA negative/not detected: eligible

^a It is recommended that patients who are receiving potentially immunosuppressive therapy and are IgG HBcAb positive and HBV DNA negative undergo surveillance HBV DNA studies every 1-3 months depending upon the individual potential therapeutic risk and comorbidities. If necessary, a hepatologist should be consulted on a case-by-case basis.

Abbreviations: HBc Ab = Hepatitis B core antibody; HBs Ab = HBs Ab = Hepatitis B surface antibody; HBs Ag = Hepatitis B surface antigen; HBV DNA = Hepatitis B virus DNA; HCV RNA = Hepatitis C virus RNA.

Decision trees for the management of certain laboratory abnormalities by Sanofi are provided in [Section 17.4](#).

17.7.2.8.3.6 Dupilumab systemic exposure and immunogenicity

See [Section 9.2.2.1](#).

17.7.2.8.3.6.1 Sampling time

Predose blood samples will be collected for determination of functional dupilumab concentration in serum and anti-dupilumab antibodies (including neutralizing antibodies) on days designated in the Study Flow Chart (see [Section 17.7.2.2.2](#)). The date of collection should be recorded in the patient eCRF. The date and time also will be collected on the central laboratory requisition form and entered into the database through data transfers from the central laboratory.

In the event of any SAE or any AESI of anaphylactic reactions or systemic allergic reactions that are related to IMP and require treatment, or severe ISR lasting longer than 24 hours, samples will be collected near the onset and resolution of the event for any additional analysis if required or for archival purposes. An unscheduled systemic drug concentration page (“PK page”) in the eCRF must be completed as well.

Further follow-up of individual patients will be considered based on the overall assessment of antibody titers and clinical presentation.

17.7.2.8.3.6.2 Handling procedure

See [Section 9.2.2.1.2](#).

17.7.2.8.3.6.3 Bioanalytic method

See [Section 9.2.2.1.3](#).

17.7.2.8.3.7 Pharmacodynamics

Pharmacodynamics are the evolution of:

- Serum: Total IgE.
- FeNO.

Refer to [Section 17.7.2.2.2 Study Flow Chart](#) for the schedule of sample collection throughout this study.

Biomarkers include total IgE which will be measured with a quantitative method (for example ImmunoCAP) approved for diagnostic testing and antigen-specific IgE, which will be detected using panels of antigens appropriate to the location of the clinical site (quantitative ImmunoCAP test; Phadia).

FeNO assessment will be analyzed using a NIOX instrument (Aerocrine AB, Solna, Sweden), or similar analyzer using a flow rate of 50 mL/s, and reported in parts per billion (ppb). This assessment should be conducted prior to spirometry and following a fast of at least 1 hour. Further details on the procedure for measuring exhaled nitric oxide with NIOX will be provided in a separate instruction manual.

More detailed information on the collection, handling, transport, and preservation of samples (for example minimum volumes required for blood collection and for aliquots for each biomarker assay) will be provided in a separate laboratory manual.

17.7.2.8.4 Appropriateness of measurements

See [Section 9.4](#).

17.7.2.9 Study procedures

The substudy consists of 3 periods:

- Screening period (Visit 0).
- Open-label treatment period (52 weeks; Visits 1-10).
During the open-label treatment period, patients will continue their background therapy dose regimen used during screening period.
- Post-treatment period (12 weeks; Visit 11).

The study visits occur on the planned dates (relative to the first injection), as scheduled. The visit schedule should be adhered to within ± 3 days in the treatment period and ± 1 week for the remaining study period.

Spirometry should be done at the study site approximately the same time of the day (preferably in the morning, but it could be done at a different time of the day). Spirometry should be performed at visits as detailed in [Section 17.7.2.8.2.1](#).

Once every 2 weeks IMP administration must be separated by at least 11 days. Once every 4 weeks IMP administration must be separated by at least 25 days. The treatment period visits occur q2w up to Visit 3 (Week 4), q4w up to Visit 8 (Week 24), and approximately every 12-16 weeks up to the EOS visit as detailed in [Section 17.7.2.7.1.3](#).

See [Section 17.7.2.7.1.3](#) for Investigational medicinal product administration.

At the time of permanent treatment discontinuation, patients will perform the ETD visits including early EOT visit and early EOS visit. Early EOT will be performed 2 weeks (with a ± 3 days window) after last IMP injection whenever possible. If the time of decision taken for permanent IMP discontinuation is >2 weeks after last IMP injection, this early EOT visit should be scheduled as early as possible from permanent discontinuation of IMP decision.

All the assessments defined for the EOT Visit 10 will be performed during this early EOT. Early EOS visit will be performed 12 weeks after early EOT visit with a ± 1 week window. All the assessment defined for the EOS Visit 11 will be performed during this early EOS visit.

Patients should be reminded that sexually active patients of reproductive potential are required to practice effective contraception during the entire study duration, while taking dupilumab and for 12 weeks post last IMP dose.

Patients who discontinue early from treatment may be asked to return to the clinic to have additional ADA samples collected for analysis based on the overall assessment of antibody titers and clinical presentation at the time of discontinuation.

Recommended order of assessments: It is recommended that the order of assessments/procedures (as applicable) outlined below will be adhered to by the Investigator and site staff for every patient at each study visit at the investigative site:

1. Procedures:

a) ECG

- b) FeNO levels
- c) Spirometry

2. Safety and laboratory assessments.
3. Investigational medicinal product administration, if planned, IMP dispensation and return.
4. Controller therapy and medication withhold for next spirometry reminder.

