10.2 DEFINITION OF SOURCE DATA

Source data is all information in original records and certified copies of original records of clinical findings, observations, or other activities in a clinical trial necessary for the reconstruction and

evaluation of the trial. Source data are contained in source documents. Source documents are original documents, data and records such as hospital records, clinic and office charts, laboratory notes, memoranda, pharmacy dispensing records, recorded data from automated instruments, etc.

All the data collected in the eCRF should be transcribed directly from source documents. Data downloaded from the study-associated central laboratories, and spirometry will be considered source data.

10.3 HANDLING OF PATIENT TEMPORARY OR PERMANENT TREATMENT DISCONTINUATION AND OF PATIENT STUDY DISCONTINUATION

The IMP should be continued whenever possible. In case the IMP is stopped, it should be determined whether the stop can be made temporarily; permanent IMP discontinuation should be a last resort. Any IMP discontinuation must be fully documented in the eCRF. In any case, the patient should remain in the study as long as possible.

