10.3.4 Handling of patients after permanent treatment discontinuation

Patients will be followed-up according to the study procedures as specified in this protocol up to the scheduled date of study completion, or up to recovery or stabilization of any AE to be followed-up as specified in this protocol, whichever comes last. Study Investigators should continue background therapy after treatment discontinuation, as guided by their medical judgement.

Patients who prematurely discontinue the study medication, at the time of permanent treatment discontinuation, patients will perform:

- Early EOT visit: 2 weeks (with a ± 3 days window) after last IMP injection. If the time of decision taken for permanent IMP discontinuation is >2 weeks $+3$ days after last IMP injection, this early EOT visit should be scheduled as early as possible from permanent discontinuation of IMP decision. All the assessments defined for the EOT Visit 10 will be performed during this early EOT,
- Early EOS visit: 12 weeks after early EOT visit with a ± 1 week window. All the assessment defined for the EOS Visit 11 will be performed during this visit.

Patients who discontinue early from treatment may be asked to return to the clinic to have additional ADA samples collected for analysis based on the overall assessment of antibody titers and clinical presentation at the time of discontinuation.

All cases of permanent treatment discontinuation should be entered by the Investigator in the eCRF when considered as confirmed.

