Serum total IgE and Ag-specific IgE ^r		X							X							X			X
FeNO ^s	X	X	X	X	X	X			X							X			X

Study periods	Screening period (4±1 weeks) ^a	Open-label treatment period (52 weeks)																Post-treatment period (12 weeks)		
		Enrollment																EOT ^b		
		SOT (D1)																		
Week (W)	W-4	W0	W2	W4	W8	W12	W16	W20	W24	W28 ^c	W32 ^c	W36	W40 ^c	W44 ^c	W48 ^c	W52	W56 ^c	W60 ^c	W64	
Onsite visit ^d	0	1	2	3	4	5	6	7	8	📞	📞	9	📞	📞	📞	10	📞	📞	11	
Reminder																				
Controller and reliever therapy reminder ^c	X	X	X	X	X	X	X	X	X	X	X	X	X	X	X	X	X	X	X	
Medication withhold reminder ^c	X	X	X	X	X			X								X			X	

Abbreviations: ADA = anti-drug antibody; ACQ = Asthma Control Questionnaire; Ag specific IgE = antigen-specific IgE; D = (study) day; ECG = electrocardiogram; eCRF = electronic case report form; EOS = end-of-study; EOT = end-of-treatment; FeNO = fractional exhaled nitric oxide; IgE = immunoglobulin E; IMP = investigational medicinal product; IVRS/IWRS = Interactive Voice Response System/Interactive Web Response System; ICS = inhaled corticosteroid; LABA = long acting β 2-agonist; LAMA = long acting muscarinic antagonist; PK = pharmacokinetic; q2w = once every 2 weeks; q4w = once every 4 weeks; SOT = start-of-treatment; W = (study) week.

- a The screening period is 4±1 weeks (21-35 days) in duration to assure eligibility criteria. Prior to and during the screening period, patients must be on one of the following: stable-dose background therapy of medium-dose ICS with second controller medication (ie, LABA, LTRA, LAMA, or methylxanthines) or high-dose ICS alone or high-dose ICS with second controller, for at least 3 months with a stable dose \geq 1 month prior to the screening visit (Visit 0).
- b Patients who permanently discontinue IMP will be asked and encouraged to return to the clinic for study visits and participate in assessments according to the visit schedule until the EOS with a ±1 week window or up to recovery or stabilization of any adverse event. At the time of permanent treatment discontinuation, patients will perform the ETD visit with all the assessments defined for the EOT Visit 10.
- c Phone contact to collect safety information + reminders for IMP, controller, and reliever therapy, if appropriate reminder for withholding medication at the next visit as described in the individual visit schedules Safety information and date of phone call will be recorded in eCRF.

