17.7.2.5 Study design

17.7.2.5.1 Description of the study

This substudy is a multicenter, open-label, single arm, 1-year treatment study evaluating dupilumab given SC for a period of 52 weeks among pediatric patients in Japan. Dose regimen will be 200 mg q2w for patients with body weight >30 kg, 100 mg q2w or 300 mg q4w in 1:1 ratio for patients with body weight ≥ 15 kg and ≤ 30 kg.

Upon completion of the treatment period (or following early discontinuation of IMP), patients will continue into the post-treatment period. During the post-treatment period, patients will receive their background controller regimen based on Investigator's judgement.

For a schematic study design, please refer to [Section 17.7.2.2.1](#).

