If patients take 2 different ICS, the total daily dose of ICS should be calculated to evaluate the eligibility criteria on daily dose of ICS, which will be still considered as one controller. Please refer to medium and high-dose of ICS in [Section 17.7.2.14](#).

If the Investigator, based on his/her medical judgment, decides to optimize a patients use of asthma reliever and/or background controller medications prior to the screening visit (Visit 0), any changes in ongoing asthma medications must occur more than 1 month in advance of the screening visit (Visit 0) Day 1, in order to maintain a stable dose for at least 1 month prior to Day 1 ([Section 17.7.2.6](#)). The introduction of new controller medications must occur at least 3 months prior to Screening with a stable dose for at least 1 month ([Section 17.7.2.6](#)).

Open-label treatment period

During this period, patients will continue to take their controller medication(s) used during the screening period. The dose and baseline regimen of controller medications should not be changed, and no adjustments will be made unless the patient experiences 2 or more severe exacerbations events at any time during the study (in which case a step up of controller medication may be allowed).

Patients may be placed on systemic corticosteroids at any time as clinically indicated based on the presence of symptoms consistent with a severe asthma exacerbation event, as per the Investigator's judgment.

Post-treatment period

Upon completing the treatment period or following early discontinuation of IMP, patients will continue into the post-treatment period. During the post-treatment period, patients will receive their background controller regimen based on Investigator's judgement.

17.7.2.7.2.2 Reliever medication

See [Section 8.2.2](#).

17.7.2.7.2.3 Systemic corticosteroids

See [Section 8.2.3](#).

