1 INTRODUCTION

1.1 STUDY DESIGN

The LTS14424 Japan substudy is a multicenter, open-label, single-arm, 1-year treatment study to evaluate the efficacy, safety, and tolerability of dupilumab in Japanese pediatric participants aged 6 to <12 years with uncontrolled, persistent asthma.

For participants with body weight >30 kg, the dose regimen is 200 mg q2w. For participants with body weight \geq 15 kg to \leq 30 kg, they were randomized in a 1:1 allocation ratio to dose regimen of either 100 mg q2w or 300 mg q4w. The dose regimen determined at baseline has been maintained and will not be adjusted upon weight gain or loss during the treatment period.

After a screening phase of 4[\pm 1] weeks, participants were enrolled or randomized in the three dose regimens, and treated open-label for 52 weeks. Upon completion of the treatment period or following early discontinuation of investigational medicinal product (IMP), participants continue into a post-treatment period of 12 weeks. Thirteen participants were enrolled and a minimum of 3 participants were assigned to treatment with each of the 3 dose regimens.

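### Japan substudy: conflicting follow-up rules after a permanent IMP stop; if early visits are read as replacing planned ones, Week 12 spirometry for the primary endpoint can be lost

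*Protocol*

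**What the plan says.** Two sets of statements cover a child who stops IMP for good.

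**Visits continue.** Footnote b to the Japan flow chart asks stoppers to keep to the planned calendar as far as EOS: "Patients who permanently discontinue IMP will be asked and encouraged to return to the clinic for study visits and participate in assessments according to" [...]. It adds a single early treatment discontinuation (ETD) visit carrying the EOT assessments. Section 10.3.4, adopted for Japan by cross-reference in 17.7.2.9.3.4, opens: "Patients will be followed-up according to the study procedures as specified in this protocol up to the scheduled date of study completion". Section 17.7.2.8.3.1 says that after premature discontinuation "observations will continue until the end of the study as defined by the protocol for that patient". Section 10.3, also adopted for Japan, says: "In any case, the patient should remain in the study as long as possible".

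**Early exit.** Section 17.7.2.9 calls for an early EOT visit about 2 weeks (3 days either way) after the last injection, and then: "Early EOS visit will be performed 12 weeks after early EOT visit with a" window of 1 week either way. The rest of 10.3.4 says the same. Section 17.7.2.7.2.1 adds: "Upon completing the treatment period or following early discontinuation of IMP, patients will continue into the post-treatment period". Section 17.7.2.5.1 is similar, and the Japan SAP repeats the idea in its section 1.1: "following early discontinuation of investigational medicinal product (IMP), participants continue into a post-treatment period of 12 weeks". Section 17.7.2.9 lists Visit 11 as the visit of that period.

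Section 17.7.2.9 also says, with no exception for children off drug, that study visits take place on their planned dates counted from the first injection. No passage says which rule governs, or whether the early visits are additional to the planned ones.

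**The concern.** The Japan SAP (Table 1 and section 3.2) handles stopping IMP before Week 12 by treatment policy, uses data collected after the stop, and imputes nothing. That estimand needs Week 12 spirometry to be done in children who have stopped. A follow-up rule that can be read as ending the planned visits works against it.

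The early EOT and early EOS text in 17.7.2.9 closely follows the main-study text in section 10, where the primary endpoint is the incidence of TEAEs. In Japan the primary endpoint is a spirometry value at a fixed visit, so the same text matters more. Two other adopted sections also lean towards early exit: 10.3.3 describes withdrawal from study treatment as covering further study procedures, and 10.3.5 encourages children who no longer want IMP to complete the EOT and EOS procedures without mentioning planned visits in between.

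At stake are a missing primary value for some early stoppers and different practice between sites.

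**Working it through.** **1. The plan's own figure.** Inputs from protocol 17.7.2.10.1: SD 14.12, n = 16. Half-width = t(0.975, n−1) × SD / √n = 2.131 × 14.12 / 4 = 7.52, which reproduces the stated 7.5.

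**2. Where the early visits fall.** Spirometry windows from Japan SAP Table 7: Week 8 is Days 43–70, Week 12 is Days 71–126, Week 24 is Days 127–266. Let E be the early EOT day. Early EOS is E + 84, permitted from E + 77 to E + 91. Assume the early visits replace the planned ones and their spirometry is assigned by these windows.

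- Early EOT is too early for Week 12 if E ≤ 70.
- Nominal early EOS is too late if E + 84 > 126, so E ≥ 43. Hence Week 12 is nominally empty for E = 43–70: the early EOT maps to Week 8 and the early EOS (Days 127–154) to Week 24.
- Even the earliest permitted EOS is too late if E + 77 > 126, so E ≥ 50. Hence no permitted date helps for E = 50–70.
- An early EOT on Day 71 or later, up to Day 126, is itself in the window.

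**3. Which last doses are exposed.** With an on-time early EOT, E = last dose + 14, 3 days either way. That gives 7 EOT days × 15 EOS days = 105 permitted date combinations. They are counts of dates, not probabilities.

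| Last dose | Early EOT days | Early EOS days | Combinations with a Week 12 value |
|---|---|---|---|
| Week 0 (Day 1) | 12–18 | 89–109 | 105 |
| Week 2 (Day 15, q2w) | 26–32 | 103–123 | 105 |
| Week 4 (Day 29) | 40–46 | 117–137 | 49 |
| Week 6 (Day 43, q2w) | 54–60 | 131–151 | 0 |
| Week 8 (Day 57) | 68–74 | 145–165 | 60 |
| Week 10 (Day 71, q2w) | 82–88 | 159–179 | 105 |

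For Week 4, E = 40 to 46 leaves 10, 9, 8, 7, 6, 5 and 4 EOS days at or before Day 126, total 49. For Week 8, only E = 71 to 74 is in the window: 4 × 15 = 60.

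**4. The other readings.** Under footnote b nothing is lost. If planned visits continue until an early EOS, Week 12 is also kept: with on-time visits the earliest possible early EOS is Day 12 + 77 = Day 89, after the last permitted Visit 5 day (85 + 3 = 88). On that reading the true Week 52 visit (Day 365) is missed at nominal timing when last dose + 98 < 365, that is for last doses before Day 267.

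**5. Cost in precision.** Same formula and SD, with the 13 children enrolled (Japan SAP 1.1): n = 13 gives 8.53, n = 12 gives 8.97, n = 11 gives 9.49. One lost value costs 0.44 points and two cost 0.96.

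**The case against.** The strongest reply is that nothing cancels Week 12. Section 17.7.2.9 itself has visits taking place as planned, footnote b is written for Japan and expressly keeps the schedule, and the first sentence of 10.3.4 and section 10.3 point the same way. This stands. A reader might infer that the protocol tells sites to drop Week 12 for stoppers; the documents do not support that. The express clash is between an early EOS 12 weeks after early EOT and a scheduled EOS at Week 64. The Week 12 loss needs a further step of interpretation by the site.

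It also stands that several things must coincide: a permanent stop, an early EOT in a narrow range of days, and a site that reads the early visits as replacements. On-time early EOT after a Week 0, 2 or 10 last dose always yields a Week 12 value. The primary analysis is descriptive, and the SAP already reports the number analysed and discontinuation counts, so a gap would show.

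A reader might also infer that off-drug or re-windowed values would corrupt the endpoint. Off-drug values are legitimate under treatment policy; the issue is only a value that is never collected.

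What does not fall away is that 10.3.4 contains both rules and no text ranks them.

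**Conclusion.** The point holds as a conflict between current follow-up rules, express on EOS timing and implicit on the planned visits in between. The Week 12 consequence is conditional on the replacement reading. It also assumes that early-visit spirometry is windowed like any other and, for the results by last dose, that the early EOT is on time. The effect on precision is modest at the planning SD unless several children stop, and the documents do not say how many did. The case for acting is that one of the two rules undercuts an estimand that relies on data after the stop, and that the correction is cheap. Confidence is medium.

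**What to change.** In 17.7.2.9 and, for Japan, in 10.3.4 (through 17.7.2.9.3.4), state that footnote b governs:

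- one additional ETD visit with the EOT assessments;
- scheduled visits continue, at minimum Week 12 spirometry (Day 85, 3 days either way) and the later efficacy visits including Week 52;
- EOS stays at Week 64 unless consent for follow-up is withdrawn, with no separate early EOS for children who keep attending.

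Align the wording on moving into the post-treatment period in 17.7.2.5.1, 17.7.2.7.2.1 and Japan SAP 1.1. The Japan SAP could optionally report how many Week 12 and Week 52 values come from early visits and how many are missing after an IMP stop.

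The cost is a short clarification, by amendment or site memo, and continued visits for stoppers, which footnote b already requests. Making early EOT and early EOS both additional would be the wrong repair: footnote b asks for no early EOS, and the child would have two. For children already past Week 12 the primary value cannot be recovered; only later visits benefit.
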